Examining the feasibility and acceptability of a tailored version of a Mindfulness-Based Intervention (MBI) among YEH aged 18-25 years old

NCT04950816

Version Date: 01/15/2025

Refer to page 16, for the pilot study (Aim 3) registered as ClinicalTrials.gov record NCT04950816.

Protocol Title:	Examining the feasibility and acceptability of a tailored version of a Mindfulness-Based Intervention (MBI) among YEH aged 18-25 years old
Principal Investigator:	[name] [name], RN
Co-Investigators:	[name], [name], MHS, [name], MSW
Study Coordinator:	[name]
Population:	Homeless Youth Focus groups (n=56) Homeless Youth Working group (n=10) Pilot RCT with Youth Experiencing Homelessness ages 18-25 (n=90) Total of 156 Youth Experiencing Homelessness ages 18-25 in Houston, TX
Number of Sites:	Single site
Study Duration:	Three (3) years
Subject Duration:	Six (6) months for subjects in pilot RCT

General Information

This proposed development and pilot study will examine the feasibility and acceptability of a tailored version of a Mindfulness-Based Intervention (MBI), .b, among (Youth Experiencing Homelessness) YEH aged 18-25 years old. Building on our promising pilot research, we will work with YEH to tailor .b, including ensuring a trauma-informed approach. Using iterative beta testing with a (Homeless Youth Working Group) HYWG, we will tailor the intervention and determine appropriate methods and strategies for recruitment, adherence, and retention. Finally, we will conduct an attention control RCT pilot study of the tailored version of .b to determine feasibility and acceptability of conducting an adequately-powered RCT. We will test our recruitment/retention methods, enrollment criteria, randomization protocol, participant tracking and follow-up processes, and study measures. With the pilot, we will determine whether participants will adhere to the intervention protocol (i.e., attend sessions, complete study measures). We will determine whether the enrollment criteria appropriately identify and exclude youth who cannot safely participate in the study and if our tracking and follow-up protocol is feasible and acceptable. The results of the pilot will inform the sample size needed for a fully powered, attention control RCT of the tailored .b to provide robust and clinically useful data on intervention efficacy among YEH.

Background Information

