This study is *significant* as it lays the groundwork for a potentially beneficial program for YEH, a vulnerable, high risk, and growing population by tailoring and testing an intervention that targets the root causes of many health risk behaviors. If effective, the intervention has the potential to have far-reaching effects on youths' health and wellbeing. This scientific premise builds on the substantial body of literature that demonstrates the link between trauma, stress, maladaptive decision making, and risk behaviors and the promising effects of MBIs in high-risk youth. This *innovative* study capitalizes on established relationships with local providers and our access to this difficult-to-reach population to collaborate on tailoring of *.b* for a sheltered sample of YEH. This research aligns with NCCIH Priority Research Areas by developing and feasibility testing of a tailored MBI and evaluating its overall health and wellness impact. Data from this R34 will inform the development of an adequately-powered RCT, optimizing the recruitment and retention strategies, informing the final sample size for a larger randomized trial, and finalizing the outcome measures needed.

Study Design

This proposed study will fully develop and pilot test the feasibility and acceptability of a tailored mindfulness-based intervention among young adults experiencing homelessness ages 18-25 years old. The intervention targets stress management, emotion regulation, and impulsivity. A total of 56 homeless youth will participate in the focus group discussions (FGDs), 10 youth per session will participate and study team will consent up to 30 homeless youth for the Homeless Youth Working Group (HYWG) to account for participant drop off, 12 health and social services providers will participate in the key informant interviews, 8 service providers and 2 youth will participate on the Expert Advisory Panel (EAP), and 90 homeless youth will participate in the randomized attention control pilot study.

Expected duration of study and subject participation. Study duration is 3 years and subjects in the pilot RCT will be in the study for 6 months. Key informants and Homeless Youth Working Group will be part of the study for one year. The expert advisory panel will be in the study all three years.

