Recruitment. Given the inclusion criteria and site volume for the pilot, we expect to recruit 15 youth per arm (intervention and attention control) session for a total of 3 cohorts of 15 in each arm or 6 total groups. Based on what we've learned from previous studies with YEH, we will recruit 90 youth to deliver the intervention or control to at least 60 youth. Youth will be recruited primarily from Covenant House Texas (CHT), and homeless shelters and drop-in centers if additional recruitment sites are needed, to participate in the pilot. Youth who are eligible and enroll in the pilot study will complete a baseline survey, attend 5 90 minute sessions, complete very brief pre-post session surveys, as well as follow-up surveys immediately post-intervention and at 3 months post-intervention. Approximately 22% (n=20) of the pilot study participants will be recruited to also participate in a post-intervention exit interview. Participants will have the phone for the duration of the study. The intervention is informed by the Risk Amplification Model (RAM) and the Minority Stress Model (MSTM) and will be fully developed in Years 1-2 using a systematic intervention development process; Plan, Do, Study, and Act. In order to ascertain the feasibility and acceptability of the intervention (Aim 3), we will obtain participant feedback via exit interviews as well as quantitative implementation indicators (e.g., refusal rate, completion rates, and survey measures).

Inclusion/Exclusion of Service Providers. Key Informant Interview participants (n=12) and Expert Advisory Panel service provider members (EAP, n=8) will be health and social service providers for YEH recruited from local shelters (i.e., resident advisors, in-take specialists), drop-in centers (i.e., social workers, case managers), homeless healthcare clinics (i.e., nurses, mental health counselors, patient navigators), and the Homeless Youth Network (a network of YEH providers, of which [name] is an active member). Providers will be considered eligible if they are currently providing health or social services to YEH and are interested in participating in an interview or as a member of the Expert Advisory Panel. For those providers interested in the EAP, they will be considered eligible if they anticipate being able to meet for the regularly scheduled meetings at least 75% of the time.

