Enrollment and Data Collection Procedures. The RC and RA will recruit and enroll all participants. Once consented, the youth will take the baseline survey and receive their group assignment from the RC. A computerized randomization generator will be used. The RA will be blinded to group assignment and will conduct all data collection. For the purpose of this study, enrollment will be defined as completing consent, baseline survey, and at least one lesson of the intervention or control condition. Surveys will be completed by participants on iPads using REDCap. Participants will enter response data directly into the tablet so their answers will be private. In the case of electronic device failure, we will use back-up iPads and paper surveys and the RA will enter the responses into REDCap within 24 hours. We will use unique study IDs in the place of names to protect participant confidentiality. **Baseline and Follow-up Surveys.** Participating youth will complete surveys at baseline, immediate post-intervention, and at 3- and 6-months post-intervention. Surveys will take approximately 30 minutes to complete and will include items to measure mindfulness, perceived stress, emotion regulation, impulsivity, and mental health symptoms (see Table 2 for example measures and psychometric properties) and youth risk behaviors. We will also pilot self-report and app use to determine the most effective way to measure use of commercially available mindfulness apps. Data usage information will be gathered from mediation app on participants' phone. **Pre- and Post-Session Surveys.** Very brief pre- and post-session brief surveys will capture real-time stress, emotion regulation, positive and negative affect, mindfulness, impulsivity, and session feedback (post-session only) including likability of session content, delivery format, length, and delivery timeframe. These surveys will take approximately 5 minutes to complete prior to and immediately after each session. **Exit Interviews.** The RC will conduct individual or group exit interviews with 20 youth from the pilot study participants that will be audio-recorded and take about 30-45 minutes. We will randomly select participants from each of the 4-6 intervention cohorts to have equal representation by gender identity, age, and study group. We will elicit participant feedback on study procedures, intervention acceptability, delivery methods and strategies, barriers and facilitators of

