1. Serious events include any event or condition that is life threatening, results in a hospitalization, cancer or a physical or cardiac event serious enough to require medical attention. These events may be:
 - a. Fatal
 - b. Life threatening
 - c. Permanently disabling
 - d. Required or prolonged hospitalization (Admission—not ER visit)
 - e. Overdose
 - f. Significant hazard to patient
2. Non-Serious events includes all other events.

In addition, follow-up face-to-face visits at 3 and 6 months will include a query of subjects on whether they had “any serious health events that caused them to seek medical attention within the past 3 months,” and if any of these resulted in “hospitalizations overnight.” Details of these events will be recorded. All adverse reactions noted by any of the team members will be immediately reported to the principal investigator, the UTHealth IRB, Data Safety and Monitoring Board, and NCCIH. All adverse events will be reviewed monthly by the research team and annually by the monitoring board. Also, in keeping with NIH guidelines, minority status and gender will be included in these reports to allow for detection of differential effects.

Data and Safety Monitoring Plan. This study is considered to constitute minimal psychological and physical risk and no legal or social risks. The risks are minimal since educational interventions generally promote good health, not endanger it. Our eligibility criteria are established to exclude individuals for whom the study procedures are not appropriate. We also will screen subjects directly using validated and reliable items for collecting information on co-morbidities such as unresolved serious mental illnesses or low literacy. Using this multi-gated approach, we should be able to effectively screen out any individuals for whom this intervention is contraindicated. All health-related occurrences will be recorded and regularly reviewed by the research staff.

A few potential minimal risks to subjects exist: breach of confidentiality or normal risks associated with having a phone. Breach of confidentiality is not believed to present any significant risk given the data protections described above. However, to mitigate this risk we have outlined steps we will take to protect confidentiality in the Human Subjects sections

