Role of the Data Safety Monitoring Board. A monitoring board will review the data monitoring and safety procedures annually. This group will comprise 3 members with expertise in risk prevention, health communication, and/or homeless youth intervention research. [name] at the University of Texas Medical Branch; [name] at the University of California San Francisco Center for AIDS Prevention Studies; and [name] at the UTHealth School of Public Health will be the monitoring board members. Monitoring board meetings will be conducted annually, beginning after the first 6 months of data collection. In addition, should any adverse reaction occur, the monitoring board will be informed immediately, and a special session will be scheduled to discuss strategies to deal with the problems. The meeting will include a synopsis of protocol and design, discussion of the status of interventions and data collection procedures, a summary of subject contacts, discussion of any adverse reactions or potential adverse reactions, status of data entry and verification, and a summary of any descriptive and inferential statistics to date. However, data analyses will be conducted on each time point of data collection (baseline, immediate, 3- and 6-months post-intervention) as it is completed. In addition, the monitoring board will be given time to meet in closed session without the investigators to discuss the need for additional procedures to prevent adverse reactions or ensure data integrity or the unlikely case that the study may need an early termination due to unexpected adverse reactions or inadequate conduct of the study. Recommendations from the monitoring board meetings will be shared with the UTHealth IRB and NIH during annual reports and immediately if the monitoring board identifies adverse reactions not previously reported or recommends early termination of the study.

Role of the IRB. This study will be approved by the UTHealth IRB. The UTHealth IRB will be the primary oversight IRB for the study and the study PI ([name]) will be responsible for reporting to the IRB about the status of the study. Annual progress reports and renewals will be completed for the IRBs and

will include a summary of the recommendations of the monitoring board. If adverse reactions related to study procedures are noted, they will be immediately reported to UTH IRB by [name] so that the IRB is aware of any risks involved with the study.

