Baseline and Follow-up Survey Data. During the pilot phase, a baseline and follow-up survey will be administered at immediate post and 3 months post intervention and will take approximately 45 minutes each to complete. We will finalize the pre- and post-surveys during the development phase with the assistance of the Homeless Youth Working Group (HYWG) feedback. We anticipate including items to assess demographics (e.g., homelessness, historical factors, race/ethnicity, sexual orientation, gender identity) and behavioral outcomes. Additionally, the post-surveys will contain items measuring usability, mediating factors, and risk behaviors. To assess feasibility, we will calculate the number of eligible youth approached, participation refusal rate with reason for refusal, the number of sessions attended, follow-up survey response rates, and successful tracking methods. We will also monitor rates of recruitment and effort required (e.g., number of staff hours), number of screenings conducted and refusal rates,² and participant lost to follow up, to inform the design of a subsequent Phased Innovation Award to Optimize Mind and Body Interventions. For refusal rate, we will ask each youth we approach their age, race/ethnicity, gender identity, and sexual orientation to allow for demographic comparisons by participation status to monitor potential sample bias. Participants will be notified that no survey data will be shared with shelter and drop-in center staff or their case workers. Data will be collected on encrypted iPads using a secured REDCap system for the baseline, follow-ups, and pre-post session surveys. This data will be collected using REDCap offline at the shelter and drop-in center in order to minimize concern over data integrity in locations with weak Wi-Fi systems. Data is stored on the hard drive of the encrypted iPad and uploaded to REDCap nightly at the UTHealth office. No data from REDCap is accessible from the iPads. The tablet will be encrypted and password protected so that no one except research staff is able to gain access to the information on the tablet and the tablet is rendered useless if stolen. Only research staff will have the passwords for the REDCap database and computer. Survey data cannot be accessed from the encrypted iPad tablet and is only accessible on the REDCap secure server. Data will be downloaded from REDCap on a weekly basis and saved on secure, firewall protected hard drives.

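### The only scheduled serious-event question looks back 3 months from visits timed after the intervention, so it can miss the session period, and a missed 3-month visit leaves months 0 to 3 unasked

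*Combined protocol and SAP*

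**What the plan says.** The Adverse Event Reporting part of Data and Safety Monitoring states that "follow-up face-to-face visits at 3 and 6 months will include a query of subjects on whether they had" events of a defined kind. The item itself is worded as "any serious health events that caused them to seek medical attention within the past 3 months", followed by a question on overnight hospital stays. That section does not say what the 3 and 6 months are counted from.

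Other sections do:

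- Enrollment and Data Collection Procedures (Aim 3): "Participating youth will complete surveys at baseline, immediate post-intervention, and at 3- and 6-months post-intervention".
- Role of the Data Safety Monitoring Board, in both places where it appears: "data analyses will be conducted on each time point of data collection (baseline, immediate, 3- and 6-months post-intervention) as it is completed".
- Recruitment, under Study Population: "follow-up surveys immediately post-intervention and at 3 months post-intervention".
- Baseline and Follow-up Survey Data, under Data handling: "a baseline and follow-up survey will be administered at immediate post and 3 months post intervention".

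The last two use the same count for the 3-month visit but list no 6-month survey.

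A competing count could be inferred from the title table ("Six (6) months for subjects in pilot RCT") and from Study Design ("subjects in the pilot RCT will be in the study for 6 months"). Enrolment is defined as complete only after at least one lesson.

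No section places the serious-event question at the immediate post-intervention survey or on the pre- and post-session forms. No section sets a visit window or lengthens the recall when a visit is late or missed. Survey content is still to be finalised during the development phase.

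**The concern.** A fixed 3-month look-back gives continuous cover only if it reaches back to the previous time the question was asked, or to the start of exposure. Here the question is first asked 3 months after the intervention ends, so its look-back stops at about the last session. The period of exposure to the intervention or control sessions, which matters most when the team classifies events by attribution to the intervention, falls outside it. A missed visit opens a second hole, because the next question does not reach back over it.

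What is at stake is the completeness of serious-event capture. The comparison between arms is not at stake: both arms get the same question, and the analysis plan excludes inferential tests. The item asks about serious events that led to medical care, so the point does not rest on milder distress, which the question would not detect in any case.

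**Working it through.** The plan gives no figure on this point to reproduce. The check is interval arithmetic.

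**Inputs**

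- Recall: 3 months, taken as 91 days (assumption); 6 months is taken as 182 days.
- Sessions: 4 to 5, twice a week (Intervention Delivery, where both are described as estimates). Twice weekly is taken as alternating gaps of 3 and 4 days (assumption).
- Sample: 90 recruited. Projected drop-out: 15-20% (Role of the PI and Investigative Team). Retention benchmark: at least 50% at 3 and 6 months (Table 3).

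**Step 1. Length of delivery, first to last session**

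- 4 sessions have 3 gaps: 3+4+3 = 10 or 4+3+4 = 11 days.
- 5 sessions have 4 gaps: 3+4+3+4 = 14 days.
- Span S = 10 to 14 days.

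**Step 2. Visits counted from the last session**

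Let day 0 be the last session and L the days by which the visit is late (negative if early). The visit falls on day 91 + L, so the look-back starts on day L. Delivery runs from day −S to day 0. Days of delivery covered = min(S, max(0, −L)).

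- On time (L = 0): 0 days.
- 14 days late: 0 days, and the first 14 days after the last session are not asked about at that visit either.
- 7 days early: 7 days. 14 days early: all 10 to 14 days.

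**Step 3. Visits counted from the first session**

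The look-back now starts L days after the first session. For a visit on time or late, days covered = max(0, S − L).

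- On time: all 10 to 14 days.
- 7 days late: 10 − 7 = 3 to 14 − 7 = 7 days.
- 14 or more days late: 0 days.

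**Step 4. 3-month visit missed, 6-month visit on time**

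- Counted from the last session, the look-back covers days 182 − 91 = 91 to 182. Unasked: 91 + S = 101 to 105 days, out of 182 + S = 192 to 196 days since the first session. That is 101/192 = 53% to 105/196 = 54%.
- Counted from the first session, 91 of 182 days (50%) are unasked, and these include all of delivery.

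**Step 5. How many could be affected**

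- Projected drop-out: 0.15 × 90 = 13.5 to 0.20 × 90 = 18, so about 14 to 18 participants.
- Most missed 3-month visits the benchmark tolerates: 0.50 × 90 = 45. This is a ceiling, not a projection.
- The second gap concerns only those who miss 3 months and return at 6. The documents do not give that number, nor any event rate, so no count of missed events can be estimated.

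**The case against.** The strongest reply is that the question supplements a continuous system. Participants are told to call the study number, all health-related occurrences are to be recorded, events are reviewed monthly, and the team meets every two weeks. Delivery is also the most closely observed period: sessions are on site and twice weekly, with trained staff, shelter staff at all hours and weekday clinical care. Participant follow-up starts at enrolment to support attendance. For youth who leave or struggle with appointments, the plan offers transport vouchers, weekly walk-in times, meetings elsewhere and an escalating contact procedure.

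All of this is true and lowers the stakes. None of it is a scheduled health question. These routes still rely on someone volunteering or noticing an event, and they are weakest for participants who leave the shelter or stop attending. The plan expects some shortfall, recruiting 90 to deliver to at least 60. The Smartphone section also hands out the phone, which carries the reporting number, only after all sessions; Recruitment can be read otherwise, and the consent form carries the instructions too.

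Several narrower objections stand:

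- Counting from the last session is a reasonable reading of post-intervention timing, but the plan does not use those words.
- Session number and spacing are provisional, and respondents will not treat a spoken 3-month recall as an exact cut-off. The day counts show the pattern, not precise coverage.
- The drop-out and benchmark figures do not size the affected group, since some of these participants will never be seen again.
- Recruitment, Pilot Participant Tracking and Baseline and Follow-up Survey Data omit the 6-month survey. This conflict must be reconciled. It does not rescue the plan: without a 6-month visit, a missed 3-month visit would leave no scheduled question at all.

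**Conclusion.** The concern holds. With visits counted from the end of the intervention, as several sections have it, following the stated recall rule exactly leaves 0 of about 10 to 14 delivery days covered at an on-time or late 3-month visit. If visits were counted from the first session, the gap would close for on-time visits and reopen fully for those 14 or more days late. On either count, missing the 3-month visit leaves 3 of the 6 follow-up months unasked at an on-time 6-month visit, and delivery with them.

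This rests on reading post-intervention as after the last session, on the provisional session schedule, and on a 91-day look-back. The harm is incomplete capture of serious care-seeking events, partly offset by the unscheduled routes. It is a worthwhile improvement of low to moderate priority and does not threaten the pilot's feasibility results.

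**What to change.** 1. Ask the same question, face to face, at the in-person immediate post-intervention survey visit, with recall running from the baseline survey.
2. At 3 and 6 months, replace the fixed 3-month recall with recall since the last baseline or follow-up survey the participant completed. Staff should fill in the date, because the pre- and post-session forms are also surveys and could be mistaken for the reference point.
3. State in Adverse Event Reporting that the visits are counted from the last session, and reconcile the sections that omit the 6-month survey.
4. Enter every yes answer in the adverse-event log and tabulate by arm, descriptively. Report the length of the recall window alongside, since it will differ between participants.

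The windows then join up, and any later attended visit covers delivery and any visit missed before it.

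The cost is one more spoken item at a visit both arms already have, a wording change at two others, and a few more events to log and review. Recall becomes longer and less exact for those who miss surveys: at worst 6 months + 14 days, about 6.5 months back to the first session, plus the interval from baseline to that session. The blinded research assistant could hear group details while asking. The existing question carries that risk too, though it may be greater just after the sessions end. The item would still not capture milder distress. As survey content is not yet final, the change can be made when it is settled.
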